- ^h Vital signs include weight, temperature (oral, rectal, or tympanic), and respiratory rate. Postural vital signs (supine and standing) include pulse rate and systolic and diastolic blood pressure. At all visits, postural vital signs must be obtained after participants have been in a supine position for at least 2 to 3 minutes, followed by a standing position for at least 1 minute.
- ⁱ Clinical laboratory tests consist of clinical chemistry, hematology, and urinalysis. All laboratory tests requiring blood draws should be collected at the same time.
- ^j Urine pregnancy test will be performed in female participants of childbearing potential at Visit 1 and Visit 2 prior to dosing and at Visits 4 to 7 during study intervention. To continue in this study, a negative urine tests must be documented at Day 1 Visit (Visit 2) to start study intervention and at Visits 4 to 6 to continue study intervention. LIN-MD-64 completers who enroll in this study on the same day do not need to repeat the urine pregnancy test (Section 10.7).
- ^k The ongoing AEs from LIN-MD-64 study will be transferred to LIN-MD-66 in the auto-rollover function in EDC.
- ^l Study intervention will be administered in the clinic at the Day 1 Visit (Visit 2). On the day of this visit, all participants must fast for at least 2 hours before arriving at the clinic for their visit, where they will receive their initial dose of study intervention. Participants may eat 30 minutes after dosing (the requirement for linaclotide to be administered 30 minutes prior to any meal at the same time each day will not apply for the first dose). On all other days, it is recommended that participants take linaclotide at approximately the same time each day, 30 minutes before any meal.
- ^m Participants who took their last dose of study intervention in LIN-MD-64 on the day of the EOT Visit and enroll into LIN-MD-66 on that same day will take their first dose of LIN-MD-66 study intervention outside of the clinic at a designated time the following day. Qualified site personnel will complete a follow-up phone call to participants within 48 hours following initial study intervention administration to assess safety.
- ⁿ The number of bottles of study intervention that should be dispensed at each visit is as follows: V2 (1 bottle), V4 (1 bottle), V5 (2 bottles), and V6 (2 bottles). The bottles will be assigned via IWRS.

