- ^j Study intervention will be administered in the clinic at the Day 1 Visit (Visit 2). On the day of this visit, all participants must fast for at least 2 hours before arriving at the clinic for their visit, where they will receive their initial dose of study intervention. Participants may eat 30 minutes after dosing (the requirement for study intervention to be administered 30 minutes prior to any meal at the same time each day will not apply for the first dose). On all other days, it is recommended that participants take linaclotide at approximately the same time each day, 30 minutes before any meal.
- ^k The ongoing AEs from LIN-MD-62 will be entered in the eCRF. The ongoing AEs from LIN-MD-64 will be transferred to LIN-MD-66 in the auto-rollover function in EDC.
- ^l The number of bottles of study intervention that should be dispensed at each visit is as follows: V2 (1 bottle), V4 (1 bottle), V5 (2 bottles), and V6 (2 bottles).
- ^m Additional unscheduled visits may be allowed at the discretion of the investigator with approval from the sponsor.
- ⁿ Rome III assessment at Screening will be assessed over the 2 month period immediately prior to the LIN-MD-66 Screening Visit (Visit 1), or over the 1 month period immediately prior to the LIN-MD-66 Screening Visit if 2 months have not elapsed.

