^f Fecal impaction is defined as a hard mass in the lower abdomen identified on physical examination or a dilated rectum filled with a large amount of stool on rectal examination. If fecal impaction is documented during an optional repeat physical examination, the sponsor must be notified. If a rectal examination is performed, the medically qualified site personnel should assess for and document the presence of anal wink and normal anal tone.

^g A fecal impaction assessment is performed at the study Day 1 Visit (Visit 2) prior to study intervention administration. If the participant is impacted at Visit 2, the participant would not be eligible for the study.

^h Vital signs include weight, temperature (oral, rectal, or tympanic), and respiratory rate. Postural vital signs (supine and standing) include pulse rate and systolic and diastolic blood pressure. At all visits, postural vital signs must be obtained after participants have been in a supine position for at least 2 to 3 minutes, followed by a standing position for at least 1 minute.

ⁱ Clinical laboratory tests consist of clinical chemistry, hematology, and urinalysis. All laboratory tests requiring blood draws should be collected at the same time.

^j Urine pregnancy test will be performed in female participants of childbearing potential at Visit 1 and Visit 2 prior to dosing and at Visits 4 to 10 during study intervention. To continue in this study, a negative urine test must be documented at Day 1 Visit (Visit 2) to start study intervention and at Visits 4 to 9 to continue study intervention. LIN-MD-63 and LIN-MD-64 completers who enroll in this study on the same day do not need to repeat the urine pregnancy test (Section 10.7).

- ^k The ongoing AEs from LIN-MD-63 will be entered in the eCRF. The ongoing AEs from LIN-MD-64 study will be transferred to LIN-MD-66 in the auto-rollover function in EDC.
- ^l Study intervention will be administered in the clinic at the Day 1 Visit (Visit 2). On the day of this visit, all participants must fast for at least 2 hours before arriving at the clinic for their visit, where they will receive their initial dose of study intervention. Participants may eat 30 minutes after dosing (the requirement for linaclotide to be administered 30 minutes prior to any meal at the same time each day will not apply for the first dose). On all other days, it is recommended that participants take linaclotide at approximately the same time each day, 30 minutes before any meal.

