- Review any AEs occurring after assent/consent is obtained. Ongoing AEs from the prior study should be entered into the eCRF.

Participants who enroll into LIN-MD-66 from LIN-MD-63 or LIN-MD-64 within \leq 28 days of last study intervention may have the Screening (Visit 1) combined with Study Day 1 (Visit 2).

- Obtain informed consent for participants who turn 18 and enroll within \leq 28 days of the last study intervention.
- Obtain urine pregnancy test in female participants of childbearing potential. Participants from LIN-MD-63 or LIN-MD-64 studies who enroll in this study on the same day as their EOT Visit in the lead-in study do not need to repeat the urine pregnancy test (Section 10.7).

In addition, for Phase 2 LIN-MD-62, LIN-MD-63, and Phase 3 LIN-MD-64 study intervention completers who enroll in LIN-MD-66 $>$ 28 days from last study intervention, the following procedures will be performed at Screening (Visit 1):

- Complete Rome III assessment
- Instruct participants and caregivers about lifestyle modifications: increased water and fiber intake, increased physical activity, and consistent toileting habits.
- Perform a complete physical examination, including, at a minimum: general appearance, skin, HEENT (head, ears, eyes, nose, and throat), neck, thorax/lungs, cardiovascular, abdomen, musculoskeletal, lymph nodes, neurologic (including mental status), and visual inspection of the lumbosacral and perianal region. Breast and genitourinary examinations are optional at the discretion of the investigator
- Obtain height, vital signs (weight, temperature [oral, rectal, or tympanic], and respiratory rate), and postural vital signs (supine and standing systolic and diastolic BP and pulse rate) (Section 8.2.2)
- Obtain standard 12-lead ECG (supine)
- Obtain clinical laboratory tests consisting of clinical chemistry, hematology, and urinalysis (see Table 10-1); all laboratory tests requiring blood draws should be collected at the same time
- Obtain serum β -hCG pregnancy test for female participants of childbearing potential.

- Obtain a urine drug screen at Screening (Visit 1) for all participants 12 to 17 years of age; a urine drug screen will be obtained for participants 6 to 11 years of age only if deemed necessary by the investigator. Urine drug screens may be repeated at the investigator's discretion at any time during the study.

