9.2.1 Treatment-Emergent Adverse Events

An AE will be considered a treatment emergent adverse event (TEAE) if:

- The AE began on or after the date of the first dose of study intervention in LIN-MD-66; or
- The AE was present before the date of the first dose of study intervention in LIN-MD-66 but increased in severity or became serious on or after the date of the first dose of study intervention in LIN-MD-66.

However, an AE that occurs more than 30 days after the last dose of study intervention in LIN-MD-66 will not be counted as a TEAE.

An AE will be considered a treatment emergent serious adverse event (TESAE) if it is a TEAE that additionally meets any serious adverse event (SAE) criterion.

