9.2.7 Diarrhea Treatment Emergent Adverse Events

The TEAE summary by SOC and PT will be provided for those subjects who had a TEAE of diarrhea, regardless of whether these TEAEs occurred concurrently.

The following information will be summarized for the subjects who had a diarrhea TEAE. Each diarrhea TEAE for each subject shall be counted as a separate event for the summaries described in the first 2 bullets below.

- The number and percentage of subjects with a 1 or more diarrhea TEAE events, with 2 or more diarrhea TEAE events, and with 3 or more diarrhea TEAE events.
- The number and percentage of diarrhea TEAEs with an end date, and ongoing at the end of the study.
- Descriptive statistics for the time to onset of the first diarrhea TEAE. The number and the percentage of subjects with diarrhea TEAE will be summarized by time to onset of first occurrence using the following time intervals: Day 1, Day 2, Day 3-7, Week 2 to Week 11 (for each week), and Week 12 and later.
- The longest duration of diarrhea TEAEs within a subject will be summarized. For those subjects with at least one diarrhea TEAE ongoing at the end of the study, the subject will be counted in the 'Ongoing' category. The number and the percentage of subjects classified according to their longest diarrhea duration or ongoing will be summarized by the following duration intervals: 1 day, 2 days, 3-7 days, 8-14 days, 15-28 days, >28 days, and ongoing. The descriptive statistics for the duration of the longest duration of diarrhea TEAE with an end date for subjects will be presented.

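### Lead-in diarrhea that continues unchanged into LIN-MD-66 is in no planned summary of diarrhea incidence or duration, yet adds full treatment time to the EAIR denominator

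*Protocol*

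**What the plan says.** **Transfer of open events.** For FC children entering within 28 days of their last lead-in dose, Protocol 1.4 (Table 1-1, footnote k) states: "The ongoing AEs from LIN-MD-64 study will be transferred to LIN-MD-66 in the auto-rollover function in EDC". Protocol 1.5 (Table 1-3, footnote k) repeats this for IBS-C children from LIN-MD-64 and adds for the Phase 2 study: "The ongoing AEs from LIN-MD-63 will be entered in the eCRF". The Visit 1 instructions in Protocol 10.10.1 agree: "Ongoing AEs from the prior study should be entered into the eCRF". Table 1-2 carries the LIN-MD-64 rule for later entrants: "The ongoing AEs from LIN-MD-64 will be transferred to LIN-MD-66 in the auto-rollover function in EDC".

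**Treatment-emergent rule.** SAP 9.2.1 has two routes. The first is onset: "The AE began on or after the date of the first dose of study intervention in LIN-MD-66; or". The second is for events already present: "The AE was present before the date of the first dose of study intervention in LIN-MD-66 but increased in severity or became serious". Protocol 9.4.1 uses the same two routes.

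**Scope of the tables.** The AE overview (SAP 9.2.2), the tables by SOC and preferred term (9.2.3) and the exposure-adjusted incidence rate, EAIR (9.2.4), are built on TEAEs. So is the diarrhea section: "The following information will be summarized for the subjects who had a diarrhea TEAE", and "The longest duration of diarrhea TEAEs within a subject will be summarized". In the EAIR, a child without the event contributes the full treatment duration as time at risk.

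**The concern.** Long-term safety is the only objective, and the protocol asks for particular attention to diarrhea (Protocol 8.3). How long diarrhea persists on continued treatment is part of that. A child whose diarrhea starts on linaclotide in the lead-in and runs unchanged through 24 or 52 further weeks has the longest duration this study could observe, yet SAP 9.2.7 leaves that child out. A new one-day episode is counted.

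The case is realistic for early rollovers. Protocol 4.1 provides for a last lead-in dose on the end-of-treatment day and a first LIN-MD-66 dose the next day. IBS-C children from LIN-MD-64 may stay on the same blinded dose. Exclusion criterion 1.01 removes a child with an unresolved AE only if the investigator sees a reason to. Diarrhea in both Phase 2 studies was mostly mild and never severe (Protocol 2.2.2), so it may well pass that filter.

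The rule also sits uneasily with other SAP choices for the same children. Their baseline for laboratory values, vital signs, weight, height and ECG is the lead-in baseline (SAP 9.1), and linaclotide exposure is summed across the two studies (SAP 6.0). Adverse events alone restart at the first LIN-MD-66 dose.

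**Working it through.** The plan gives no figure for this point, so there is none to reproduce. The check applies the SAP rule to cases, then illustrates scale.

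**1. The rule applied to four cases (SAP 9.2.1)**

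| Diarrhea record | TEAE? |
|---|---|
| Carried over, unchanged | No |
| Carried over, severity increases after first dose | Yes |
| Carried over, becomes serious after first dose | Yes |
| New episode with onset after first dose | Yes |

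Only the first case is lost. It adds 0 to diarrhea incidence, to the over-28-days and ongoing duration categories, and to the counts of ended and ongoing events.

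**2. EAIR contribution (SAP 9.2.4)**

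EAIR = 100 × children with the event / (total days at risk / 365.25). A carried-over, unchanged case adds 0 to the numerator. At full follow-up it adds 168/365.25 = 0.46 patient-years (FC) or 364/365.25 = 1.00 patient-years (IBS-C) to the denominator, although a child who already has diarrhea is not at risk of a first occurrence.

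**3. How many children**

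- Planned enrollment: at least 120 (SAP 2.4).
- Lead-in diarrhea on linaclotide: 7.6%, from LIN-MD-62 (Protocol 2.2.2), borrowed for scale.
- Share still ongoing at entry: not in the documents; 10% to 50% assumed.

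120 × 0.076 × 0.10 = 0.9 and 120 × 0.076 × 0.50 = 4.6, so about 1 to 5 children if all 120 came from linaclotide. If half came from placebo (assumption), 60 × 0.076 × 0.10 = 0.5 and 60 × 0.076 × 0.50 = 2.3. Exclusions under criterion 1.01 would lower either range.

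**4. Effect on the summaries**

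Further assumptions: 5 new diarrhea TEAEs among 120 children, each on Day 14, full follow-up otherwise, and k carried-over unchanged cases.

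| | k = 1 | k = 5 |
|---|---|---|
| Crude incidence under the SAP, 5/120 | 4.2% | 4.2% |
| Any diarrhea on treatment, (5 + k)/120 | 5.0% | 8.3% |
| EAIR under the SAP, 168 days | 9.42 | 9.42 |
| EAIR, carried-over cases out of risk set, 168 days | 9.50 | 9.85 |
| EAIR under the SAP, 364 days | 4.36 | 4.36 |
| EAIR, carried-over cases out of risk set, 364 days | 4.39 | 4.55 |

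For example, at 168 days with k = 5: SAP days at risk = 5 × 14 + 115 × 168 = 19,390, giving 100 × 5 / (19,390/365.25) = 9.42. With the 5 cases removed, 5 × 14 + 110 × 168 = 18,550, giving 9.85.

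Correcting the denominator raises the EAIR by only about 1% to 5%. The larger loss is in the count of children with diarrhea on treatment and, above all, in the duration picture.

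**The case against.** The strongest defence is that onset-or-worsening is a usual TEAE definition for an extension study. Protocol and SAP state those two routes alike, and the study is descriptive with no hypothesis. That stands: nothing is miscalculated, and the definition need not change.

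The gap is also narrower than it first looks. Protocol 8.3 and 10.3.1 treat a change in frequency of an existing condition as reportable, so a flare recorded as a new AE after the first dose would count. What remains is the uninterrupted, essentially unchanged event.

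Three stronger readings are tempting, and the documents do not support them.

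- *A reader might infer that these cases can be seen only in a listing.* They are in the listing of all AEs (SAP 9.2.3). They may also appear in the displays of all AEs for children with potentially clinically significant laboratory, vital-sign or ECG values (SAP 9.3 to 9.5). The AESI table (SAP 9.2.6) is not worded as TEAE-only. None of these, however, summarizes how many children have persistent diarrhea or for how long.
- *A reader might infer that, in children entering after more than 28 days, diarrhea returning on re-dosing would hide under an old open record.* That needs sites to leave resolved events open. AEs are reviewed at Visits 1 and 2 (Protocol 10.10.1, 10.10.2), and a return after the first dose has a new onset date and so is a TEAE.
- *A reader might want a percentage of all on-treatment diarrhea that is missed.* That needs an assumed new-onset rate as well as an assumed ongoing share. The one documented rate comes from LIN-MD-62, whose completers appear only in the schedule for entry after 28 days. The documents do not support such a percentage.

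**Conclusion.** The point holds for children who roll over within 28 days. On the plan's own wording, lead-in diarrhea that continues without increasing in severity or becoming serious is absent from TEAE incidence, the EAIR numerator and all of SAP 9.2.7, while the child counts as event-free time in the EAIR. No planned table fills the gap. The omission can only make diarrhea on long-term treatment look less frequent and shorter.

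The size is unknown. The figure of about 1 to 5 of 120 children rests on a rate borrowed from another lead-in study, an assumed 10-50% still ongoing at entry, all children having come from linaclotide, and no exclusions under criterion 1.01. The number is lower if any of those who enter came from placebo, as some FC children from LIN-MD-64 may. This is a gap in the description of the drug's main adverse event, worth closing because it costs little.

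**What to change.** Keep the TEAE definition and all TEAE tables as they are, and add three items.

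1. **SAP 9.2:** one supplementary table of AEs ongoing at the first LIN-MD-66 dose, by preferred term, severity and lead-in treatment (linaclotide or placebo), with outcome (resolved, or ongoing at the end) and days persisting on LIN-MD-66 drug.
2. **SAP 9.2.7:** a separate row, labelled as carried over from the lead-in, in the incidence, longest-duration and ongoing summaries, kept apart from the TEAE counts.
3. **SAP 9.2.4:** for the diarrhea EAIR, remove from the risk set the children whose diarrhea is ongoing at first dose, or give that result as a sensitivity analysis.

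The events are already in the database through the rollover and eCRF entry. The cost is one extra table, a few rows and one extra rate. The downside for the sponsor is a slightly less favourable diarrhea picture.

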1.5. Schedule of Activities (SoA) for IBS-C Participants

Table 1–3 Schedule of Activities - Phase 2 Study LIN-MD-63 and Phase 3 Study LIN-MD-64 IBS-C Completers Who Enroll in Study LIN-MD-66 Within \leq 28 Days From the Last Study Intervention

Study Periods (Duration)	Screening (Up to 14 days)	Study Intervention Period (52 weeks)								
		Day 1	Week 2	Week 4	Week 8	Week 16	Week 24	Week 32	Week 40	Week 52 Visit/ EOT
Study Visit ^o	Screening	2	3	4	5	6	7	8	9	10
Visit Number	1									
Study Day	-14 to -1 ^{a,b}	1 ^b	15 (\pm 3) ^c (Phone Visit)	29 (\pm 3)	57 (\pm 3)	113 (\pm 3)	169 (\pm 3)	225 (\pm 3)	281 (\pm 3)	365 (+3) ^d
Study Procedure										
Parent/caregiver consent/assent	X									
Inclusion and exclusion criteria	X	X								
Rome III assessment										X
IWRS	X	X		X	X	X	X	X	X	
Medical history	X									
Physical examination ^e										X
Fecal Impaction assessment ^f	X	X ^g								
Vital signs, and postural vital signs ^h		X		X	X	X	X	X	X	X
Height										X
Electrocardiogram										X
Prior and concomitant medication	X	X	X	X	X	X	X	X	X	X
Clinical laboratory tests ⁱ										X
Urine pregnancy test ^j	X	X		X	X	X	X	X	X	X
Study intervention administration in the clinic ^l		X ^m								

Study Periods (Duration)	Study Intervention Period (52 weeks)									
	Screening	Day 1	Week 2	Week 4	Week 8	Week 16	Week 24	Week 32	Week 40	Week 52 Visit/ EOT
Study Visit ^o	Screening	2	3	4	5	6	7	8	9	10
Visit Number	1									
Study Day	-14 to -1 ^{a,b}	1 ^b	15 (± 3) ^c (Phone Visit)	29 (± 3)	57 (± 3)	113 (± 3)	169 (± 3)	225 (± 3)	281 (± 3)	365 (+3) ^d
Adverse event evaluation ^k	X	X	X	X	X	X	X	X	X	X
Study intervention dispensed ⁿ		X		X	X	X	X	X	X	
Study intervention compliance and accountability				X	X	X	X	X	X	X

^a Study procedures for screening may be combined with EOT Visit in study LIN-MD-63 or LIN-MD-64.

^b Provided there is no fecal impaction at Screening (Visit 1), study procedures for Screening (Visit 1) and Day 1 Visit (Visit 2) may be combined.

^c Week 2 visit will be a phone visit for all participants.

^d All enrolled participants who prematurely discontinue from the study, regardless of cause, are required to return for the EOT study assessments.

^e Physical examinations will be performed by medically qualified site personnel at Visit 10 and may be done at the investigator's discretion at any time.

^f Fecal impaction is defined as a hard mass in the lower abdomen identified on physical examination or a dilated rectum filled with a large amount of stool on rectal examination. If fecal impaction is documented during an optional repeat physical examination, the sponsor must be notified. If a rectal examination is performed, the medically qualified site personnel should assess for and document the presence of anal wink and normal anal tone.

^g A fecal impaction assessment is performed at the study Day 1 Visit (Visit 2) prior to study intervention administration. If the participant is impacted at Visit 2, the participant would not be eligible for the study.

^h Vital signs include weight, temperature (oral, rectal, or tympanic), and respiratory rate. Postural vital signs (supine and standing) include pulse rate and systolic and diastolic blood pressure. At all visits, postural vital signs must be obtained after participants have been in a supine position for at least 2 to 3 minutes, followed by a standing position for at least 1 minute.

ⁱ Clinical laboratory tests consist of clinical chemistry, hematology, and urinalysis. All laboratory tests requiring blood draws should be collected at the same time.

^j Urine pregnancy test will be performed in female participants of childbearing potential at Visit 1 and Visit 2 prior to dosing and at Visits 4 to 10 during study intervention. To continue in this study, a negative urine test must be documented at Day 1 Visit (Visit 2) to start study intervention and at Visits 4 to 9 to continue study intervention. LIN-MD-63 and LIN-MD-64 completers who enroll in this study on the same day do not need to repeat the urine pregnancy test (Section 10.7).

- ^k The ongoing AEs from LIN-MD-63 will be entered in the eCRF. The ongoing AEs from LIN-MD-64 study will be transferred to LIN-MD-66 in the auto-rollover function in EDC.
- ^l Study intervention will be administered in the clinic at the Day 1 Visit (Visit 2). On the day of this visit, all participants must fast for at least 2 hours before arriving at the clinic for their visit, where they will receive their initial dose of study intervention. Participants may eat 30 minutes after dosing (the requirement for linaclotide to be administered 30 minutes prior to any meal at the same time each day will not apply for the first dose). On all other days, it is recommended that participants take linaclotide at approximately the same time each day, 30 minutes before any meal.
- ^m Participants who took their last dose of lead-in study intervention in LIN-MD-63 or LIN-MD-64 on the day of the EOT Visit and enroll into LIN-MD-66 on that same day will take their first dose of LIN-MD-66 study intervention outside of the clinic at a designated time the following day. Qualified site personnel will complete a follow-up phone call to participants within 48 hours following initial study intervention administration to assess safety.
- ⁿ The number of bottles of study intervention that should be dispensed at each visit is as follows: V2 (1 bottle), V4 (1 bottle), V5 (2 bottles), V6 (2 bottles), V7 (2 bottles), V8 (2 bottles), and V9 (3 bottles). The bottles will be assigned via IWRS.
- ^o Additional unscheduled visits may be allowed at the discretion of the investigator with approval from the sponsor.

Table 1-4 Schedule of Activities – Phase 2 Study LIN-MD-63 and Phase 3 Study LIN-MD-64 IBS-C Completers Who Enroll in LIN-MD-66 After > 28 Days From Last Study Intervention

Study Periods (Duration)	Screening (Up to 14 days)	Study Intervention Period (52 weeks)									
	Screening	Day 1	Week 2	Week 4	Week 8	Week 16	Week 24	Week 32	Week 40	Week 52 Visit/ EOT	
Study Visit ^m	Screening	Day 1	Week 2	Week 4	Week 8	Week 16	Week 24	Week 32	Week 40	Week 52 Visit/ EOT	
Visit Number	1	2	3	4	5	6	7	8	9	10	
Study Day	-14 to -1	1	Day 15 (± 3) ^a (Phone Visit)	Day 29 (± 3)	Day 57 (± 3)	Day 113 (± 3)	Day 169 (± 3)	225 (±3)	281 (±3)	365 (+3) ^b	
Study Procedure											
Parent/caregiver consent/assent	X										
Inclusion and exclusion criteria	X	X									
Rome III assessment	X ⁿ									X	
IWRS	X	X		X	X	X	X	X	X		
Medical history	X										
Lifestyle modifications review	X										
Physical examination ^c	X									X	
Fecal impaction assessment ^d	X	X ^e									
Vital signs, and postural vital signs ^f	X	X		X	X	X	X	X	X	X	
Height	X									X	
ECG	X									X	
Prior and concomitant medication	X	X	X	X	X	X	X	X	X	X	
Clinical laboratory tests ^g	X									X	
Urine drug screen ^h	X										
Serum pregnancy test ⁱ	X										
Urine pregnancy test ^j		X		X	X	X	X	X	X	X	

Study Periods (Duration)	Study Intervention Period (52 weeks)									
	Screening (Up to 14 days)	Day 1	Week 2	Week 4	Week 8	Week 16	Week 24	Week 32	Week 40	Week 52 Visit/ EOT
Study Visit^m	Screening	Day 1	Week 2	Week 4	Week 8	Week 16	Week 24	Week 32	Week 40	Week 52 Visit/ EOT
Visit Number	1	2	3	4	5	6	7	8	9	10
Study Day	-14 to -1	1	Day 15 (± 3)^a (Phone Visit)	Day 29 (± 3)	Day 57 (± 3)	Day 113 (± 3)	Day 169 (± 3)	225 (±3)	281 (±3)	365 (+3)^b
Study Procedure										
Study intervention administration in the clinic ^j		X								
AE evaluation ^k	X	X	X	X	X	X	X	X	X	X
Study intervention dispensed ^l		X		X	X	X	X	X	X	
Study intervention compliance and accountability				X	X	X	X	X	X	X

^a Week 2 visit (Visit 3) will be a phone visit for all participants.

^b All enrolled participants who prematurely discontinue from the study, regardless of cause, are required to return for the EOT study assessments.

^c Physical examinations performed by medically qualified site personnel at Visits 1 and 10 may be repeated at the investigator's discretion.

^d Fecal impaction is defined as a hard mass in the lower abdomen identified on physical examination or a dilated rectum filled with a large amount of stool on rectal examination. If fecal impaction is documented during an optional repeat physical examination, the sponsor must be notified. If a rectal examination is performed, the medically qualified site personnel should assess for and document the presence of anal wink and normal anal tone.

^e A fecal impaction assessment is performed at the study Day 1 Visit (Visit 2) prior to study intervention administration. If the participant is impacted at Visit 2, the participant would not be eligible for the study.

^f Vital signs include weight, temperature (oral, rectal, or tympanic), and respiratory rate. Postural vital signs (supine and standing) include pulse rate and systolic and diastolic blood pressure. At all visits, postural vital signs must be obtained after participants have been in a supine position for at least 2 to 3 minutes, followed by a standing position for at least 1 minute.

^g Clinical laboratory tests consist of clinical chemistry, hematology, and urinalysis. All laboratory tests requiring blood draws should be collected at the same time.

^h The urine drug screen will be obtained at Screening (Visit 1) for all participants 12 to 17 years of age and, only if deemed necessary by the investigator, for participants 7 to 11 years of age.

- ⁱ A pregnancy test will be obtained for female participants of childbearing potential. Serum β -hCG will be performed at Screening (Visit 1), while urine pregnancy test will be performed at Visits 2 and 4 to 10 during study intervention. To continue in this study, a negative serum test must be documented at the Screening Visit (Visit 1) and negative urine tests must be documented at Day 1 Visit (Visit 2) to start study intervention and at Visits 4 to 9 to continue study intervention.
- ^j Study intervention will be administered in the clinic at the Day 1 Visit (Visit 2). On the day of this visit, all participants must fast for at least 2 hours before arriving at the clinic for their visit, where they will receive their initial dose of study intervention. Participants may eat 30 minutes after dosing (the requirement for study intervention to be administered 30 minutes prior to any meal at the same time each day will not apply for the first dose). On all other days, it is recommended that participants take linaclotide at approximately the same time each day, 30 minutes before any meal.
- ^k The ongoing AEs from LIN-MD-63 will be entered in the eCRF. The ongoing AEs from LIN-MD-64 study will be transferred to LIN-MD-66 in the auto-rollover function in EDC.
- ^l The number of bottles of study intervention that should be dispensed at each visit is as follows: V2 (1 bottle), V4 (1 bottle), V5 (2 bottles), V6 (2 bottles), V7 (2 bottles), V8 (2 bottles), and V9 (3 bottles). The bottles will be assigned via IWRS.
- ^m Additional unscheduled visits may be allowed at the discretion of the investigator with approval from the sponsor.
- ⁿ Rome III assessment at Screening will be assessed over the 2 month period immediately prior to the LIN-MD-66 Screening Visit (Visit 1), or over the 1 month period immediately prior to the LIN-MD-66 Screening Visit if 2 months have not elapsed.

2. Introduction

Linaclotide is a 14-amino acid peptide that acts on the apical surface of epithelial cells surrounding the intestinal lumen to stimulate the guanylate cyclase subtype C (GC-C) receptor. Linaclotide is approved for the treatment of irritable bowel syndrome with constipation (IBS-C) and chronic idiopathic constipation (CIC) in the United States, Canada, Japan, Australia, New Zealand, Kingdom of Saudi Arabia, and Mexico; for the treatment of IBS-C in China, the European Union (EU), Hong Kong, Macau, and Switzerland; and is being studied in other regions. By activating GC-C, orally administered linaclotide has been found to increase intestinal fluid secretion and intestinal transit, and to decrease visceral (abdominal) pain. Linaclotide has minimal oral bioavailability ($\leq 0.2\%$) in several animal species (Bryant 2010; Eutamene 2010) and is minimally absorbed with low systemic availability in adults. Refer to the Investigator's Brochure (IB) for a more detailed description of the chemistry, pharmacology, efficacy, and safety of linaclotide, based on studies conducted in animals, healthy volunteers, and in participants with IBS-C and CIC (linaclotide IB).

Two Phase 2 dose-ranging studies have been conducted with linaclotide in pediatric participants; one in FC, 6 to 17 years of age (LIN-MD-62), and one in IBS-C, 7 to 17 years of age (LIN-MD-63). Results from these two studies are summarized in Section 2.2.2.

This study will assess the long-term safety of linaclotide administered to pediatric participants with FC (total exposure with linaclotide for 24 weeks) or IBS-C (total exposure with linaclotide for 52 weeks) who have completed Study LIN-MD-62, LIN-MD-63, or LIN-MD-64:

- LIN-MD-62 (Phase 2): A Multicenter, Randomized, Double-blind, Placebo-controlled, Parallel-group, Safety and Efficacy Study of a Range of Linaclotide Doses Administered Orally to Children, Ages 6 to 17 Years, Who Fulfill Modified Rome III Criteria for Child/Adolescent FC
- LIN-MD-63 (Phase 2): A Multicenter, Randomized, Double-blind, Placebo-controlled, Parallel-group, Safety and Efficacy Study of a Linaclotide Dose Administered Orally to Children, Ages 7 to 17 Years, With Irritable Bowel Syndrome With Constipation (IBS-C) (ie, Fulfill Rome III Criteria for Child/Adolescent IBS and Fulfill Modified Rome III Criteria for Child/Adolescent Functional Constipation)
- LIN-MD-64 (Phase 3): A Phase 3, Multicenter, Randomized, Double-blind, Parallel-group, Safety and Efficacy Study of Linaclotide in Pediatric Participants, Ages 6 to 17 Years, With Irritable Bowel Syndrome with Constipation (IBS-C) and of Linaclotide versus Placebo in Pediatric Participants with Functional Constipation (FC)

